#### 7.2 PARTICIPANT DISCONTINUATION/WITHDRAWAL FROM THE STUDY

Participants are free to withdraw from participation in the study at any time upon request.

Participants will be withdrawn according to protocol for the following reasons:

- Other medical diagnosis typically associated with significant weight loss (5% or more of body weight). In addition to malignancy, examples include nonmalignant gastrointestinal disease, endocrinopathies, infectious disease, rheumatologic diseases, etc. As [name] (study Co-I, general internist) will be blinded to participants' study group assignment, he will adjudicate in these situations, seeking consultation from medical colleagues as appropriate.
- New diagnosis of medical condition such that participation in a behavioral weight loss intervention is no longer appropriate.
- Permanent change in living situation (e.g. from home to nursing home) such that the participant has limited food options.

Pregnancy: Study participants who become pregnant may continue to participate in the study with the understanding that weight loss goals will be suspended during pregnancy through 3 months postpartum. If a pregnant participant wishes to continue with counseling session during pregnancy, the focus on counseling will be on dietary quality. The participant may resume full participation 3 months postpartum. Any data collected while the participant is pregnant will be censored and follow-up data will not be collected until the participant is 6 months postpartum.

A participant will be considered lost to follow-up if we are unable to contact him/her according to this algorithm.

- Attempts at telephone contact:
  - We will call up to 5 times over a 2 week period. We will attempt 2 calls during regular work hours (8:30 to 5:30 on weekdays) and 3 after hours, including Mon-Thurs evening between 5:31 and 9:00 pm and on Saturday calling between 8:30 and 5:30 pm.
  - We will leave up to 2 phone messages.
  - If no contact is made over this initial 2 week period as outlined above, we will undertake more limited contact attempts for an additional 2 weeks including up to 2 phone calls per week, 1 during business and the other during evening hours or on the weekend.
- Email: If a participant gives us permission to contact by email, we will send up to 4 weekly emails.
- Text: If a participant gives us permission to contact by text, we will send up to 4 weekly texts.
- Alternative contact: During enrollment, we will collect information on an alternative contact that we are given permission to contact. We will attempt to contact this individual up to 3 times a week for 4 weeks.

No replacement is planned for those who withdraw from the intervention for the study.

### 7.3 LOST TO FOLLOW-UP

A participant will be considered lost to follow-up if we are unable to contact him/her according to this algorithm.

- Telephone contact:
  - We will call up to 5 times over a 2 week period. We will attempt 2 calls during regular work hours (8:30 to 5:30 on weekdays) and 3 after hours, including Mon-Thurs evening between 5:31 and 9:00 pm and on Saturday calling between 8:30 and 5:30 pm.
  - We will leave up to 2 phone messages.
  - If no contact is made over this initial 2 week period as outlined above, we will undertake more limited contact attempts for an additional 2 weeks including up to 2 phone calls per week, 1 during business and the other during evening hours or on the weekend.
- Email: If a participant gives us permission to contact by email, we will send up to 4 weekly emails.
- Text: If a participant gives us permission to contact by text, we will send up to 4 weekly texts.
- Alternative contact: During enrollment, we will collect information on an alternative contact that we are given permission to contact. We will attempt to contact this individual up to 3 times a week for 4 weeks.

If we are unable to contact a participant as outlined above, a letter will be sent to the current mailing address and inviting the participant to contact us if he/she still wishes to participate in this study.

Should the participant continue to be unreachable and does not respond to the mailed letter within 4 weeks, he or she will be considered to have withdrawn from the study with a primary reason of lost to follow-up.

## 8 STUDY ASSESSMENTS AND PROCEDURES

## 8.1 ENDPOINT AND OTHER NON-SAFETY ASSESSMENTS

Study data will be collected at baseline, and 3 months. Process data will be collected as part of the intervention via the web-based platform by counselors immediately after sessions.

OBJECTIVES	ENDPOINTS	JUSTIFICATION FOR ENDPOINTS	Collection Time (min)	Data Collection times (month)			
				0	1	2	3
Primary				X		X	X
Primary Aim: To test the feasibility of implementing and acceptability of an online family dyadic/couple skills	Feasibility will be measured by the number of participants who consent, and the percent of dyads that attend both sessions.  Acceptability will be measured by a satisfaction survey complete by both dyad members	Primary Outcome	1  15				X
Secondary			45				
Secondary Aim: To explore the experience of administering a family dyadic/couple skills training online from a counselor perspective (i.e., facilitators, barriers, acceptability).							X

- **Physical examination-based assessments (e.g., weight)**
- At study outset, weights (seven 50 pound weights) assessed and adjusted for accuracy on 12/3/19 by North Carolina Department of Agriculture and Consumer Services Standards Laboratory.

- Weights to be re-assessed and adjusted for accuracy annually.
- Scales tested for accuracy the first week of each month during their use in this study.

**Seca 874 dr Scale Tolerance Testing**  
*(updated 1/28/20)*

The scale's 6 AA batteries should be replaced at least once a year.

It is **imperative** that tolerance weights be handled carefully (no slamming around or banging against one another) to maintain their accuracy.

Before starting the test set the **ON-OFF** switch to **ON**. Press the **start** key with no load on the scale. If necessary switch the weight display from **kg** to **lbs** by pressing the **2 in 1** key for approximately 3 seconds.

- 1) Place a 50 lb wt in the center of the scale and record weight. (~50 lbs) Remove the 50 lb wt. Press **start** key.
- 2) Carefully stack two 50 lb wts on top of one another in the center of the scale. The first weight must be gently vibrated until the second is in place to prevent the scale from prematurely locking in and giving an erroneous reading. Record the weight reading (~ 100 lbs). Press the **2 in 1** key.
- 3) Place a third 50 lb wt on the scale and record weight. (~50 lbs The sum of this weight and the weight observed in step 2, ~ 100 lbs, is the observed reading for the expected weight of 150 lbs) **Remove the top 50 lb wt. only.**
- 4) Place two 50 lb wts on top of the two remaining weights vibrating the stack as before. Record the weight reading (~ 100 lbs The sum of this weight and the weight observed in step 2, ~ 100 lbs, is the observed reading for the expected weight of 200 lbs). Remove all four weights. Press **start** key.
- 5) Carefully, but quickly, stack five 50 lb wts on top of one another in the center of the scale, gently but firmly vibrating the stack until the fifth weight is added. Record the weight reading (~ 250 lbs). Press the **2 in 1** key.
- 6) Place a sixth 50 lb wt on the scale and record weight. (~50 lbs The sum of this weight and the weight observed in step 6, ~ 250 lbs, is the observed reading for the expected weight of 300 lbs) **Remove the top 50 lb wt. only.**
- 7) Place two 50 lb wts on top of the five remaining weights vibrating the stack as before. Record the weight reading (~ 100 lbs The sum of this weight and the weight observed in step 6, ~ 250 lbs, is the observed reading for the expected weight of 350 lbs). Remove all weights.
- 8) Set **ON-OFF** switch to **OFF**.

During the testing if any observed reading falls outside the tolerance range repeat the testing steps to verify the reading. No need to continue testing the scale if a weight is out of range and verified. Scales failing the tolerance testing should no longer be used.

lbs	0.40%	
	Tolerance	
	Limit	Range
50	0.2	49.8 - 50.2
100	0.4	99.6 - 100.4
150	0.6	149.4 - 150.6
200	0.8	199.2 - 200.8
250	1	249.0 - 251.0
300	1.2	298.8 - 301.2
350	1.4	348.6 - 351.4

**Scale S/N** \_\_\_\_\_

**Date** \_\_\_\_\_

Expected Weight (lbs.)	Observed Weight (lbs.)	Difference (lbs.)	0.40% Tolerance Limit (lbs.)
50	_____	_____	0.2
100	_____	_____	0.4
(50)	_____	_____	
150	_____	_____	0.6
(100)	_____	_____	
200	_____	_____	0.8
250	_____	_____	1
(50)	_____	_____	
300	_____	_____	1.2
(100)	_____	_____	
350	_____	_____	1.4

## WEIGHT MEASUREMENT PROTOCOL

*(last updated 10/28/19)*

Prior to the appointment the participant is instructed to wear light clothing and informed that the weight measurements will be made with shoes removed.

### Materials

- Seca model 874 dr electronic personal scale

### Preparation

- Place the scale on a hard level surface.
- Turn the scale ON with the ON-OFF switch. Press the start key with no load on the scale. The scale is automatically set to zero and ready for use.
- Once the digital display reads zero **verify that “lbs” unit is showing**. If “kg” appears in the display press the 2 in 1 key for approximately 3 seconds. “lbs” should then show in the display.

### Procedure

#### Participant

- With shoes removed, scale displaying zero; step onto the middle of the scale.
- Stand on both feet, knees extended (straight) with arms by sides.

#### Research Staff

- Once the reading in the digital display is stable, record the first weight on the Weight Measurement Form in lbs, **recording the tenths of lb** (i.e. 81.4 lbs).
- Have the participant step off the scale.
- Have the participant step back onto the scale once zero is displayed. **Note:** You may need to restart the scale by pressing the start key to obtain the zero and lbs display before instructing the participant to step back onto the scale.
- Once the reading in the digital display is stable, record the second weight on the form.
- Record the difference between the first and second readings.
- If the **difference is greater than 1 lb repeat** and record a third weight.
- When finished weighing participants turn the scale OFF with ON-OFF switch.

#### Note

- A stabilized reading in the scale display is needed for recording. The participant needs to stand very still while breathing naturally. If moving too much the weight will not stabilize in the display.

#### Scale Accuracy Testing

- To insure accuracy the scales have been tested using certified tolerance weights. (Performed by research center staff each month).
- Staff should weigh themselves whenever the scale is set up for participant measurement

#### Scale Care

- Treat the scale as a laptop. Do not bump against other objects or expose to extreme temperatures.
- Store in the horizontal position without stacking anything on top.

- Do not allow anyone to weigh without your supervision and instructions.
- When not using, turn the ON-OFF switch to OFF to conserve the battery.
- *Performance-based assessments (e.g., physical function – gait, balance; sensory testing – pain perception, proprioception; neuropsychological/cognitive assessments – dementia assessment, executive function, memory performance tests)*
- *Administration of questionnaires, interviews, or other instruments for patient (or other, e.g., family, caregiver-) reported outcomes, such as a daily diary*

### Collecting questionnaire data

- See Section 5.5, Strategies for Recruitment and Retention, which outlines how eligibility and baseline questionnaires will be administered.
- In brief, at the outset of the study, participants will complete questionnaires on-line using the qualtric interface.
- The data collection windows are 2 weeks before baseline, and 3 month follow-up.

## 8.2 SAFETY ASSESSMENTS

As noted, this study is considered minimal risk. The following safety procedures are included as part of this protocol.

- As part of the physical activity intervention, an information sheet on safety while being active will be provided.
- A participant will be withdrawn from the study if they lose more than 15 lbs over the course of the month due to non-intervention protocol reasons. Participant will be instructed to contact their PCP to determine if additional evaluation is warranted for underlying medical disease that may be contributing to weight loss.

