### 2.3.2 KNOWN POTENTIAL BENEFITS

Research is designed to benefit society by gaining new knowledge. A benefit from being in this study is improvement in lifestyle and losing weight. However, some not benefit from being in this study

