## 8.3 ADVERSE EVENTS AND SERIOUS ADVERSE EVENTS

### 8.3.1 DEFINITION OF ADVERSE EVENTS

This protocol uses the definition of adverse event from 21 CFR 312.32 (a): any untoward medical occurrence associated with the use of an intervention in humans, ***whether or not considered intervention-related.***

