#### 8.3.3.2 RELATIONSHIP TO STUDY INTERVENTION/EXPERIMENTAL MANIPULATION

All adverse events (AEs) will have their relationship to study procedures, including the intervention, assessed by an appropriately-trained clinician based on temporal relationship and his/her clinical judgment. The degree of certainty about causality will be graded using the categories below.

- **Definitely Related** – There is clear evidence to suggest a causal relationship, and other possible contributing factors can be ruled out. The clinical event, including an abnormal laboratory test result, occurs in a plausible time relationship to study procedures administration and cannot be explained by concurrent disease or other drugs or chemicals. The response to withdrawal of the study procedures should be clinically plausible. The event must be pharmacologically or phenomenologically definitive.
- **Probably Related** – There is evidence to suggest a causal relationship, and the influence of other factors is unlikely. The clinical event, including an abnormal laboratory test result, occurs within a

reasonable time after administration of the study procedures, is unlikely to be attributed to concurrent disease or other drugs or chemicals, and follows a clinically reasonable response on withdrawal.

- **Potentially Related** – There is some evidence to suggest a causal relationship (e.g., the event occurred within a reasonable time after administration of study procedures). However, other factors may have contributed to the event (e.g., the participant's clinical condition, other concomitant events). Although an AE may rate only as "possibly related" soon after discovery, it can be flagged as requiring more information and later be upgraded to "probably related" or "definitely related", as appropriate.
- **Unlikely to be related** – A clinical event, including an abnormal laboratory test result, whose temporal relationship to study procedures administration makes a causal relationship improbable (e.g., the event did not occur within a reasonable time after administration of the study procedures) and in which other drugs or chemicals or underlying disease provides plausible explanations (e.g., the participant's clinical condition, other concomitant treatments).

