#### 8.3.4 TIME PERIOD AND FREQUENCY FOR EVENT ASSESSMENT AND FOLLOW-UP

Solicited potential adverse events will occur at each visit and follow-up measurement visit. They include the following and we will ask if evaluation for these events included emergency room visit or overnight hospital stay.

- Acute myocardial infarction
- Angina pectoris
- Stroke
  - Thrombotic
  - Hemorrhagic
- TIA
- Heart failure
- Coronary bypass surgery
- Cancer
  - Type of cancer
- Broken bone
  - Type of fracture
- Light headedness or dizziness
- Pneumonia
- Other infection
  - UTI
  - Other
- Hypoglycemia
  - Other

Unsolicited adverse events (AE) or serious adverse events (SAE) may come to the attention of study staff during counseling visits, phone calls, or via other channels of communications. They will be categorized as above and entered into the appropriate follow-up questionnaire at the time of occurrence.

Information to be collected about AEs and SAEs includes event description, time of onset, study clinician's assessment of severity, relationship to study procedures (assessed only by those with the training and authority to make a diagnosis), and time of resolution/stabilization of the event. All AEs occurring while on study will be documented appropriately regardless of relationship. All AEs will be followed to adequate resolution.

Any medical or psychiatric condition that is present at the time that the participant is screened will be considered as baseline and not reported as an AE. However, if the study participant's condition deteriorates at any time during the study, it will be recorded as an AE.

Changes in the severity of an AE will be documented to allow an assessment of the duration of the event at each level of severity to be performed. Documentation of onset and duration of each episode will be maintained for AEs characterized as intermittent.

Study staff will record events with start dates occurring any time after informed consent is obtained until the last day of study participation.

---

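### On its natural reading, 8.2 gives the PCP instruction only after a loss of more than 15 lb in a month has been put down to causes outside the programme, so a rapid loss credited to the programme carries no mandatory referral

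*Combined protocol and SAP*

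**What the plan says.** Section 8.2 deals with rapid weight loss in one bullet of two sentences. Under the first, someone enrolled is to be "withdrawn from the study if they lose more than 15 lbs over the course of the month due to non-intervention protocol reasons". Under the second, that person is to be "instructed to contact their PCP to determine if additional evaluation is warranted for underlying medical disease that may be contributing to weight loss". The bullet does not say who decides that a loss has a cause outside the programme, or how.

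Other sections bear on the point:

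- **7.2** lists as a ground for withdrawal "Other medical diagnosis typically associated with significant weight loss (5% or more of body weight", closing the bracket there. Of the general-internist co-investigator, who is blinded to arm, it says that "he will adjudicate in these situations, seeking consultation from medical colleagues as appropriate".
- **2.3.2** says: "A benefit from being in this study is improvement in lifestyle and losing weight".
- **8.3.1** defines an AE as "any untoward medical occurrence associated with the use of an intervention in humans", and adds that this holds whether or not the event is thought to be related to the intervention.
- **8.3.3.2** has the relationship of every AE to study procedures "assessed by an appropriately-trained clinician based on temporal relationship and his/her clinical judgment".
- **8.3.4** lists events to be asked about at each visit, allows for unsolicited events, requires AEs to be documented whatever their relationship to the study, and says: "All AEs will be followed to adequate resolution".

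**The concern.** The PCP contact is meant to find out whether disease contributes to the loss. On the natural reading of 8.2 it is offered only once the loss has been attributed to something other than the programme, so the conclusion comes before the inquiry. A participant who loses weight fast in a weight loss programme may have the loss credited to the programme, and 8.2 then prescribes no step. If that credit is mistaken, an undiagnosed illness could be missed at the one place in 8.2 designed to look for it.

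What is at stake is the safety of an individual participant. No statistical result of the trial depends on it.

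**Working it through.** The plan gives no figure to reproduce here. The check is a reading of the text, with some arithmetic for scale and for whether the fix can be carried out.

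**1. Two readings of the bullet.** Take a loss of more than 15 lb in a month.

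| Cause as judged by staff | PCP sentence tied to the first sentence | PCP sentence standing alone |
|---|---|---|
| Outside the programme | withdraw, PCP | withdraw, PCP |
| Credited to the programme | no step in 8.2 | PCP |
| Not yet settled | no step until settled | PCP |

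The readings differ in the second and third rows. The second sentence follows directly in the same bullet, refers simply to the participant and states no condition. That makes the tied reading the more natural one, but the wording does not exclude the other.

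**2. Other routes for a loss credited to the programme.**

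- 7.2 starts from a medical diagnosis. It does not prompt a search for one that has not been made.
- 8.3.1 and 8.3.4 do not exclude an event because it is credited to the programme. The loss must, however, first be seen as untoward, and 2.3.2 counts losing weight as a benefit. Whether staff would see a loss of this size as untoward is left open.
- The solicited list in 8.3.4 includes light-headedness or dizziness, hypoglycemia, infection and cancer. Weight loss is not on it.
- The unsolicited route in 8.3.4 is general and has no weight trigger.
- 6.5 assesses medication at each study visit, which may also bring a cause to light.

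These routes can catch the loss, but none of them requires PCP contact because of it.

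**3. Size of the limit.** The 15 lb is from 8.2. A month is taken as 30 days, and the start weights are assumed, since the documents give none.

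- Weekly rate: 15 × 7 / 30 = 3.5 lb.
- Share of body weight: 15 / 200 = 7.5%; 15 / 250 = 6.0%; 15 / 300 = 5.0%.
- Weight at which 15 lb equals 5%: 15 / 0.05 = 300 lb.

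Below 300 lb, a loss over the 8.2 limit therefore exceeds 5% of body weight, the figure that 7.2 attaches to disease-related loss. This is for scale only. The 5% in 7.2 has no time frame and describes diagnoses. It is not a limit for an individual participant.

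**4. Weights available for a size-only trigger.** The schedule in 1.3 marks weight at every visit. Nominal days from Visit 1 to the Post Assessment are 1, 7, 14, 21, 35, 49, 79 and 91, so the gaps are 6, 7, 7, 14, 14, 30 and 12 days. All seven are 30 days or less, so with no missed visit no extra weighing is needed. Baseline has no day number and is left out.

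The ±7-day windows can stretch the gap from Visit 6 to Visit 7 to (79 + 7) − (49 − 7) = 86 − 42 = 44 days.

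**5. Applying the 15 lb limit to weights further apart.** The implied rate falls as the gap grows:

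- 44 days: 15 × 7 / 44 = 2.4 lb a week.
- 56 days (Visit 5 to Post Assessment, 91 − 35): 15 × 7 / 56 = 1.9 lb a week.
- 90 days (Visit 1 to Post Assessment, 91 − 1): 15 × 7 / 90 = 1.2 lb a week.

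Without a cap on the interval, the rule would refer gradual losers as if their loss were rapid.

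**The case against.** The strongest reply is that the bullet need not be read narrowly. The PCP sentence carries no cause condition, and its purpose, to look for disease that might be contributing, suits a cause that is still unsettled. If it covers any loss above 15 lb in a month, there is no gap. This stands as far as it goes: the text is ambiguous. But staff could then apply the same safety rule in two ways, which is itself a reason to reword it.

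The second reply is that the AE rules apply regardless of relationship, that a clinician assesses causality, that AEs are followed up, and that symptoms and medication are asked about at visits. Applying 8.2 at all also means that someone considers the cause of the loss. This stands too. A reader might infer that a rapid loss credited to the programme will go unevaluated, or that the plan lacks clinicians or AE follow-up. The documents support neither. What is missing is a mandatory PCP referral.

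A reader might also infer that crediting the programme is the likeliest error of attribution. The documents give no rate of misattribution in either direction, so this is not claimed.

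**Conclusion.** The point holds as a minor, cheap improvement to a safety rule. On the natural but not the only reading of 8.2, the PCP instruction reaches only participants whose loss of more than 15 lb in a month has already been attributed to causes outside the programme. A rapid loss credited to the programme then carries no mandatory PCP referral, although general AE routes and solicited symptoms may still pick it up.

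The conclusion rests on that reading and on the absence of a PCP requirement for such a loss elsewhere in the plan. The percentages rest on assumed start weights. The number of participants affected cannot be estimated from the documents. The feasibility and acceptability results do not change.

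It is tempting to set the 5% in 7.2 against the 15 lb in 8.2 as conflicting thresholds. They serve different purposes, and no contradiction is claimed.

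**What to change.** Reword the bullet in 8.2 so that the referral depends on size of loss and the attribution comes afterwards:

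> Any participant who loses more than 15 lb between study weights taken up to about a month apart is told to contact their PCP, whatever the suspected cause. The general-internist co-investigator (7.2) then judges the cause, taking account of any PCP result. The participant is withdrawn only if the cause is outside the programme.

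Study weights should mean those measured on the study scale. The Quality Assurance and Quality Control section has eligibility data gathered remotely from participants, so a pre-screening weight would not count.

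Two things should stay out of the rewording. AE recording should remain with 8.3.1 and 8.3.4, regardless of relationship, because a condition on cause would contradict both. The 15 lb limit should not be carried over to weights much more than a month apart, since over 90 days it would refer someone losing about 1.2 lb a week.

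The cost is protocol wording. The weights, the visits and the co-investigator are already in the plan. The downside is an occasional unnecessary PCP contact. One limit remains: 6.2.1 collects visit weights only if available, and a missed visit or a stretched window can leave no pair of weights about a month apart. The trigger is then silent, and the general AE routes remain.
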